## **Appendix D. RiskSEARCH Interview Schedule**

Thank you for agreeing to speak to me today about your experience in the study. In this interview I would like to discuss your views of the COVID-19 study which you have been taking part in, how you found the experience, and what impact it had on you.

The interview should take about 40 minutes, but if you want to take a break or stop at any time just tell me and we can stop immediately. You don't have to answer any question you don't want to, so if that is the case, just say so and we can move on to something else.

There are no right or wrong answers.

I'd like to reassure you, again, of confidentiality. Any information you give us will be used anonymously - your name will not be attached to the transcripts of this interview or included in any reports of our findings from these interviews.

Please feel free to add anything that you think is important but which I may not ask you about. It is only by talking to people in this way, can we develop a monitor that is really useful to you and other people who are in a similar situation to you in the future.

I'd like to make sure you have had an opportunity to read the Informed Consent Form which we sent you by email. Do you have any question about the Informed Consent Form? Have you read it and do you have questions about it? Do you consent to being interviewed? In particular, are you happy that your anonymous data can be stored and shared with other genuine researchers (this is not necessary for interview to take place)? Are you happy to proceed with the interview?

### **Context**

1. What led you to sign up for the study?

### **Study**

2. We are interested in hearing about your views on the enrollment process, for example, navigating the website, completing the online eligibility questionnaire, talking to a study team member to give consent, getting the device and setting it up, etc. How was this process for you? (Prompt: barriers)
3. Are you still involved with/participating in the COVID-19 study? If not, why?

4. Have there been any negative effects of taking part in the study?
5. What did you think about the following COVID-19 study stuff?
  - a. Website
  - b. Emails from the study team
  - c. Calls with the study team
  - d. \$100 for participating
  - e. Other?
6. What was the best and the worst thing about taking part in the study?

### **Community by Current Health website**

7. When you used the Community by Current Health website, could you tell me more about when and how often?
  - a. How long did you use it for?
  - b. If you stopped, why?
  - c. What ideas do you have for encouraging people to keep using it?
8. Tell me about your experience using the website.
  - a. Was the information helpful?
  - b. Was the layout usable?
  - c. What would you like to have seen?
  - d. What were your patterns of use?
  - e. Were there issues with the design?
9. Aside from this study, can you tell us about anything else you've used or done to contribute to COVID-19 research?

### **Wearable Device**

10. Have you had any challenges in receiving, setting up the device or wearing it?
11. Have you had any technical issues?
  - a. If so, have you received the support you needed to resolve the issues?
12. If you have had periods of time you have not worn the device, could you tell me why that is? (prompt: times of days or activities that led to removing the device)
13. What have you liked about wearing the device?
14. What have you disliked about wearing the device?
15. What could make using and wearing the device easier or more engaging?

**Tablet**

16. Have you had any challenges in using the tablet?
17. Have you had days you missed answering the survey and if so, what contributed to these?
18. What have you liked about the tablet?
19. What could make using the tablet easier to use or more engaging?
20. When setting up the kit, did you follow the printed guide, the on-tablet guide, or both?
21. Were the instructions on the tablet to fill in the questionnaire clear? Are there any improvements that we should consider?
22. Are there any other features you would like to see added to the tablet device?
23. We're about to finish up. Now is your opportunity to share any other feedback or thoughts you have about the study.

Thank you for your time today. We will send payment to you through PayPal.

## 1. Administrative Information

### 1.1. SAP Version

SAP Version	Date
1	December 14 th , 2020
2	January 11 th 2021
3	February 10 th , 2021

### 1.2. Protocol Version

Protocol Version	Date
1	November 23 rd , 2020
2	December 18 th , 2020
3	January 21 st , 2021

### 1.3. SAP Revisions

The revisions in this draft SAP have been redlined with track changes and dates in addition to previous versions kept in a version controlled cloud environment.

### 3. Abbreviations and Definitions

BMI	Body Mass Index
BN	Bayesian Network
CH	Current Health
CRA	Clinical Research Associate
CRF	Case Report Form
DP	Designated Person
IMP	Investigational Medical Product
NOK	Next of Kin
Risk SEARCH	Risk Stratification and Early Alerting Regarding COVID-19 Hospitalization
SAP	Statistical Analysis Plan

### 4. Introduction

#### 4.1. Preface

In the proposed research, we will use Current Health's remote monitoring wearable device to create novel algorithms to help us predict the progression and severity of COVID-19 in individuals that have recently become infected in the community. Risk scores based on demographics, or for patients in hospital, already exist. However, by using continuous remote patient monitoring, in combination with machine learning and data analysis, we hope to predict the risk of an individual infected with COVID-19 requiring hospitalization, intensive care unit (ICU) treatment, or death based on their vital signs while still in the community.

Using a hospital-grade home-based, remote monitoring wearable gives us the opportunity to create a unique and extremely useful tool in predicting and managing the clinical effects of the COVID-19 pandemic. Our algorithm might bridge the gap between demographic models and in-hospital models of disease progression by providing real-time data from the community. If we are successful, this tool could be made available immediately to enable better resource allocation for patients after diagnosis. In addition, it enables patient-centered management, increasing confidence for low and high-risk patients, and those managing their care. The results of this research will provide a database that can be used in future trials to assess treatment efficacy and offer the potential for rapid algorithm iteration in the event of a future pandemic.

## 4.2. Scope of the analyses

These analyses will assess the model robustness and predictive performance for primary and secondary outcomes (5.1) in COVID-19 PCR or antigen positive participants.

# 5. Study Objectives and Endpoints and Hypotheses

## 5.1. Study Objectives, Endpoints, and Outcomes

The overall objective of this study is to train, develop, validate and release a digital biomarker-based algorithm that, in COVID-19 PCR or antigen positive participants, within 30 days of a positive test:

1. Primary Outcomes:
  - a. Predicts likelihood of requiring a stay in hospital of at least 24 hours
  - b. Predicts likelihood of recovery from COVID-19 defined as:
    - i. For asymptomatic participants: 14 days without symptoms following positive test
    - ii. For symptomatic: at least 14 days since onset of symptoms, with the last three days symptom free
2. Secondary Outcomes:
  - a. Predicts likelihood of being admitted to ICU for either non-invasive (CPAP, BiPAP, high flow nasal oxygen), invasive ventilation or vasopressor support.
  - b. Predicts likelihood of death.
3. Tertiary Outcomes: Successful delivery, setup, daily interface engagement, and compliance with wearing of the device

## 5.2. Statistical Hypotheses

These study methods are designed to create an algorithm, specifically a Bayesian Network (BN), and then test the statistical accuracy of the developed Bayesian Network and comparison models on the primary and secondary outcomes. The model acceptance criteria and stated hypothesis is the model's ability to predict the primary outcome of hospitalization of study participants with 75% accuracy. The secondary outcomes will be more exploratory with less strict acceptance criteria. The ability to successfully predict secondary outcomes will largely depend on the number of secondary outcomes observed and if it warrants adequate power.

The benchmarks of model performance will be as follows: AUC between 0.50 and 0.55 is poor, 0.55 to 0.65 is moderate, 0.65 to 0.75 is acceptable, and >0.75 is excellent. Brier scores will be used to verify the accuracy of the event prediction during calibration, where a perfect score is 0 and imperfect score is 1. Brier scores will be calculated for each individual prediction, representing one study participant, and an aggregate Brier score for the sequence of predictions of the participant set.

Different specificity and sensitivity levels will need to be considered when creating a feature that automatically triggers notification of study staff to reduce number of unnecessary alarms and alarm fatigue. In addition, the duration of time a patient spends in a high-risk state needs to be considered. For example, if a participant's oxygen saturation levels (SpO2) levels decrease for a brief period, then regain to normal levels, we will evaluate this to determine if it is an indicative of

patient deterioration or not. This will likely be undertaken by generating a rolling average or median of a certain number of time periods,  $t$ , to ascertain a confident deterioration event.

If the model performs statistically significantly better than 75% (AUC >0.75) with reasonable specificity, sensitivity, and calibration the model will be finalized and deployed.

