## **Stage 2**

### *Testing Stage – Expansion for Model Creation or Validation*

To assess the algorithm performance, algorithm testing on a total of 1,000 participants will be conducted. This cohort of 1,000 testing participants will be held entirely separate from the

training participants to minimize data snooping bias in the study. In machine learning, it is typical to obtain initial testing cohort results to determine if the model created from the training data is performing well. After the first 100 participants in the testing cohort are monitored for 30 days, the algorithm will be tested for understanding initial performance. As more participants are recruited into the study, follow-up algorithm testing will occur for each 100 participants that are added to the testing cohort.

Although the outcome of the participants in the validation set is known, the outcomes will be initially ignored, as if researchers did not know participant outcome. This simulates what researchers know about a participant, preceding the participant's outcome. The testing participants' collected variables (demographic, medical history, continuous data from wearable, and symptom data) will be run through the developed Bayes network algorithm and comparison models. The algorithm will return probabilities of the study outcomes. The algorithm's probabilities will then be compared with the true outcome of the participant recorded by the study team.

The differences between the algorithm prediction and participant's true outcome will be used to calculate performance metrics such as positive predictive value (PPV), area under the curve/receiver operating characteristic (AUC/ROC), and Brier scores. The final part of algorithm validation will be calibration analysis, sensitivity analysis, and determining any subpopulations that may have had poor predictive performance.

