The benchmarks of model performance will be as follows: area under curve between 0.50 and 0.55 is poor, 0.55 to 0.65 is moderate, 0.65 to 0.75 is acceptable, and >0.75 is excellent. Brier scores will be used to verify the accuracy of the event prediction during calibration, where a perfect score is 0 and imperfect score is 1. Different specificity and sensitivity levels will need to be considered when creating a feature that automatically triggers notification of study staff that a participant is likely (probability of hospitalization >50%) to reduce alarm and alarm fatigue. In addition, the duration of time a patient spends in a high-risk state needs to be considered. For example, if a participant's oxygen saturation levels (SpO2) levels decrease for a brief period, then regain to normal levels, we will evaluate this to determine if it is an indicative of patient deterioration or not.

We hypothesize that our model will achieve an accuracy of 75% or higher.

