## 6.4. Statistical Analyses and Stopping Guidance

Analyses will be conducted in three distinct parts of the trial. Analysis following the pilot study of 50 participants including feasibility, adherence rates, univariate and bivariate statistics, and informing structural design of the Bayesian Network. Descriptive statistics will include univariate analysis such as frequency, box plots, or histograms, and where appropriate, bivariate analysis on covariates using methods such as regression, Fisher's exact tests, or chi-squared analyses.

Stages 1 and 2 are covered in more depth (9.1) but generally following a training and testing machine learning design, respectively. Stopping guidance is determined by both recruitment feasibility and model performance. After a total of 2050 participants are reported, the recruitment will stop. If the model performs statistically significantly better than 75% (AUC >0.75) with reasonable specificity, sensitivity, and calibration, the model will be finalized and deployed. Benchmarks were established as reasonable for similar outcomes in literature. If the model does not meet this standard, we will conduct further analysis into where performance failures were most pervasive to decide how performance could best be improved. Adjustments to significance levels due to analysis stages are not relevant to Bayesian methods.

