To assess the algorithm performance, algorithm testing on a total of 1,000 participants will be conducted. This cohort of 1,000 testing participants will be held entirely separate from the training participants to avoid any possible data snooping or data mining bias in the study. In machine learning it is typical to obtain initial testing cohort results to determine if the model created from the training data is performing well. After the first 100 participants in the testing cohort are monitored for 30 days, the algorithm will be tested for understanding initial performance. As more participants are recruited into the study, follow up algorithm testing will occur for each 100 participants that are added to the testing cohort. To avoid any potential issues with multiple testing, only the most recent testing metrics (AUC/ROC, PPV, Brier Scores, etc.) will be reported. Therefore, the unique full test set will only be run *once*.

Although the outcome of the participants in the validation set is known, the outcomes will be initially ignored, as if researchers did not know participant outcome. This simulates what researchers know about a participant preceding the participant's outcome. The testing participants' collected variables (demographic, medical history, continuous data from wearable, and symptom data) will be run through the developed algorithm. The algorithm will return probabilities of the study outcomes. The algorithm's probabilities will then be compared with the true outcome of the participant recorded by the CRA.

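### The stated hypothesis of 75% accuracy is met by a model that predicts no hospitalisations (90% accurate at the planned 10% event rate), and it is not the same rule as AUC above 0.75

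*Combined protocol and SAP*

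**What the plan says.** SAP 5.2 introduces its target with the words "The model acceptance criteria and stated hypothesis is" and then gives it as the model's "ability to predict the primary outcome of hospitalization of study participants with 75% accuracy". The protocol, at the end of its Stage 2 section, says: "We hypothesize that our model will achieve an accuracy of 75% or higher". That sentence does not mention AUC.

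The last paragraph of SAP 5.2 gives a deployment rule: "If the model performs statistically significantly better than 75% (AUC >0.75) with reasonable specificity, sensitivity, and calibration the model will be finalized and deployed". SAP 6.4 repeats it and adds that, if the standard is not met, the reasons for poor performance will be analysed.

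Neither document defines accuracy or sets a classification cut-off for it in the text available. The only probability threshold is the above-50% figure in the protocol's Stage 2 section, which concerns a feature that notifies study staff. The Stage 2 metrics named in the protocol are PPV, AUC/ROC and Brier scores. SAP 9.2 (Stage 2) names the same three: "only the most recent testing metrics (AUC/ROC, PPV, Brier Scores, etc.) will be reported". Accuracy is not among them, although both lists are open-ended.

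**The concern.** Accuracy, in its ordinary sense, is the proportion of participants classified correctly. When few participants have the event, that proportion is dominated by those who do not, so a model can score well without identifying anyone at risk. A 75% threshold lies below what is obtained at the planned event rate with no model at all.

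AUC measures ranking and does not depend on the event rate or on a cut-off. Writing 75% and AUC 0.75 as if they were interchangeable therefore leaves two criteria that can disagree. At stake is the meaning of the study's stated hypothesis, which would be reported to the funder and in a publication.

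**Working it through.** **Inputs.** Event rate p = 10%, with 100 events in a cohort of 1,000 (protocol Data Analysis; SAP 6.3). Test cohort of 1,000 (SAP 9.2). Thresholds of 75% accuracy and AUC 0.75 (SAP 5.2, 6.4; protocol Stage 2). Significance level 0.05 (SAP 7.2), taken as two-sided because sidedness is not stated.

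**The plan's own figures.** 1,000 × 0.10 = 100 events. Calculation 1: (1.96/0.05)² × 0.1 × 0.9 = 138.3, rounded up to 139. Calculation 2: exp[(−0.508 + 0.259 ln 0.1 + 0.504 ln 30 − ln 0.05)/0.544] = 755.9, or 756. All three reproduce. None of them addresses the 75% accuracy target or the AUC target.

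**Step 1: the model that predicts no hospitalisations.** Accuracy = p × sensitivity + (1 − p) × specificity. With sensitivity 0 and specificity 1 this is 1 − p.

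| Event rate | Accuracy | AUC |
|---|---|---|
| 5% | 95% | 0.50 |
| 10% | 90% | 0.50 |
| 20% | 80% | 0.50 |
| 25% | 75% | 0.50 |

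At 10%, 900 of 1,000 are correct; the exact (Clopper-Pearson) 95% interval is 88.0% to 91.8%. Even if the target is read as significantly above 75%, only 778 of 1,000 correct are needed, so the model still passes. An AUC of 0.50 fails the deployment rule and falls in the SAP's own poor band (0.50 to 0.55).

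**Step 2: models with some information.** This step assumes a calibrated, equal-variance binormal model with p = 0.1. Let d = √2 × Φ⁻¹(AUC). A 50% probability cut-off lies at x* = ln(9)/d + d/2, so sensitivity = Φ(d − x*) and specificity = Φ(x*). The 50% value is borrowed from the notification example for illustration; the plan does not set it for the hypothesis.

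| AUC | Sensitivity | Accuracy |
|---|---|---|
| 0.60 | 0% | 90.0% |
| 0.70 | 0.5% | 90.0% |
| 0.75 | 3% | 90.1% |
| 0.80 | 11% | 90.4% |
| 0.85 | 22% | 91.1% |

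At this cut-off every model clears 75% by about 15 points, and accuracy barely separates a weak model from a good one.

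**Step 3: the opposite conflict.** Fix sensitivity at s instead; then specificity = Φ(d − Φ⁻¹(s)).

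| Fixed sensitivity | Accuracy at AUC 0.80 | Accuracy at AUC 0.85 |
|---|---|---|
| 80% | 65% | 74% |
| 70% | 74% | 81% |
| 65% | 78% | 84% |

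So a model with AUC above 0.75 can fall below 75% accuracy, depending on a cut-off the plan does not choose. The sensitivities are illustrative assumptions.

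**Step 4: what the AUC rule requires.** With the Hanley-McNeil standard error and 100 events against 900 non-events, the lower 95% limit exceeds 0.75 when the observed AUC is at least about 0.803 (0.803 − 1.96 × 0.0271 = 0.750). Power reaches 80% at a true AUC of about 0.825. SAP 7.3.2 limits testing to the adherent per-protocol population, so fewer may be analysed. If 80% are retained (80 and 720), 80% power needs a true AUC of about 0.833; if 50% are (50 and 450), about 0.852. The retained fractions are assumptions, and the event rate is held at 10%.

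**The case against.** The strongest reply is that the authors meant AUC all along. SAP 5.2 uses accuracy loosely elsewhere, for instance in describing what Brier scores verify. In both documents the hypothesis stands close to AUC benchmarks that break at 0.75, and the SAP's deployment sentence puts AUC in brackets directly after 75%. SAP 12 describes the hypothesis and the deployment standard together. On this reading there is one criterion, badly worded, and the only rule with a stated action is the AUC rule. Much of this is persuasive as to intent. It does not settle the text: no sentence defines accuracy as AUC, the protocol's hypothesis sentence omits AUC, and SAP 5.2 explicitly labels the accuracy statement the acceptance criterion.

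Second, a model with no information would not be deployed, because its AUC and sensitivity would expose it. That stands, and it limits the consequence.

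Third, SAP 12 refers to a section 9.5, while the available SAP text ends section 9 at 9.2. A cut-off may be defined in text that cannot be seen. That also stands. The remark about the missing cut-off is therefore limited to the available text, and the main point does not depend on it.

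Fourth, Steps 2 and 3 rest on an assumed model and chosen cut-offs. That is correct. Step 1 rests only on the plan's event rate and simple arithmetic, and it is enough by itself.

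**Conclusion.** The concern holds and should be fixed. The accuracy hypothesis sets a threshold 15 percentage points below what a model with no information achieves at the planned event rate, and it stays uninformative at any event rate below 25%. The AUC rule in SAP 5.2 and 6.4 is a different and sound type of criterion, and the two give opposite verdicts on the same empty model.

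The effect is confined to the hypothesis verdict and its possible disagreement with the deployment verdict; data collection, design and the deployment decision are unaffected. The core result assumes only that accuracy means the proportion correctly classified and that the 10% figure, which the plan describes as hospitalisation or intensive care treatment, serves as the hospitalisation rate, as the plan itself uses it.

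**What to change.** Use one rule throughout. In the protocol's Stage 2 section and in SAP 5.2, replace the 75% accuracy statement with the AUC rule the SAP already contains, and align SAP 6.4. Possible wording:

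> The hypothesis and acceptance criterion is a Stage 2 AUC for hospitalisation above 0.75, judged by the lower limit of a two-sided 95% interval, with reasonable specificity, sensitivity and calibration.

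The SAP should say whether that interval is a confidence or a credible interval, since 7.2 allows both. If accuracy is kept as a descriptive measure, state its cut-off and report it beside the value of 1 minus the event rate.

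Optionally, add a note to SAP 6.3 giving the observed AUC needed and the power from Step 4, with the retention assumptions stated.

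The cost is wording in three places plus the optional note. No participants or data are added. The one drawback is that the stated target will look harder to reach.

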### 6.3. Sample Size

By recruiting participants that have already been identified as SARS-CoV-2/COVID-19 positive, we expect that approximately 10% of individuals from each age group will eventually develop severe or critical COVID-19 symptoms and require hospitalization or treatment in an intensive care unit. Currently there are not sufficiently rigorous statistical models for predicting statistical power for machine learning studies. Some of the issues related to sample size for machine learning models have been recently reviewed in the scientific literature. Machine learning models can be trained to find an effect, but it is not clear if the effect is the result of over-fitting and/or poor sample selection. Nested cross-validation and calibration have been proposed to mitigate these issues. Based on extensive prior experience of our group, we expect that 100 events in continuously monitored participants will be sufficient to assess the training performance of the model for early identification of novel digital biomarkers indicative of disease severity as well as future trajectory of the severity of disease. Using the 100 events and approximate 10% event

rate, we determined that testing and training cohorts of 1,000 participants each (2,000 participants total) will be sufficient.

Although not required in observational clinical trials due to no directly measured effect size, sample size calculations were conducted under different circumstances to ensure sample is sufficiently large for a clinical prediction model.

Calculation 1: Sample size required for precise estimation of the overall outcome probability in the target population. In this study a 10% event rate has been estimated. The number of participants required under the assumption this is a true event rate where  $n$  is the required sample size,  $\phi$  is the anticipated outcome proportion, and  $\delta$  is the absolute margin of error.

$$n = \left( \frac{1.96^2}{\delta} \right) \phi(1 - \phi)$$

To estimate the required number of participants to properly observe 10% event rate at margin error of  $\leq 0.05$ :

$$n = \left( \frac{1.96^2}{0.05} \right) 0.1(1 - 0.1) = 139 \text{ participants}$$

This calculation does not represent the main goal of the study, rather is the lowest bar for number of participants for the stated event observation rate.

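### The Brier score is given only its 0 and 1 endpoints as a yardstick; at a 10% event rate the no-information value is 0.09, so the raw score cannot support the calibration condition for deployment

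*Combined protocol and SAP*

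**What the plan says.** SAP 5.2 places the Brier score among the benchmarks of model performance. It is to be "used to verify the accuracy of the event prediction during calibration, where a perfect score is 0 and imperfect score is 1". A score is computed for each participant, together with "an aggregate Brier score for the sequence of predictions of the participant set". Protocol Stage 2 gives the same scale: "where a perfect score is 0 and imperfect score is 1". AUC, by contrast, receives four graded bands.

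SAP 5.2 and 6.4 make deployment depend on performance significantly better than an AUC of 0.75, and SAP 6.4 continues: "with reasonable specificity, sensitivity, and calibration, the model will be finalized and deployed". No number or statistic defines reasonable calibration. Protocol Stage 2 lists a calibration analysis as part of the final validation step but names no statistic, plot or criterion for it.

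On the event rate, SAP 6.3 says "we expect that approximately 10% of individuals from each age group will eventually develop severe or critical COVID-19 symptoms" and, for the sample size formula, "In this study a 10% event rate has been estimated". It adds that "we expect that 100 events in continuously monitored participants will be sufficient", and on that basis that "testing and training cohorts of 1,000 participants each (2,000 participants total) will be sufficient".

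**The concern.** For a binary outcome, 0 and 1 are the correct mathematical limits of the Brier score, but they are not a useful reading scale. A forecast that carries no information about individuals scores p(1−p), which is far below 1 when the event is uncommon. Without that reference, a value such as 0.08 or 0.09 cannot be interpreted, and a fall in the event rate alone looks like an improvement.

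This matters because of where the score is used. AUC depends only on how participants are ranked, so it is unchanged if every predicted risk is too high or too low. The calibration condition has to catch that fault, and in the text available the Brier score is the only measure at the calibration stage with any stated scale. The predicted probabilities are also meant to be used as such: protocol Stage 2 contemplates notifying study staff when the predicted probability of hospitalization exceeds 50%, and names alarm fatigue as a worry.

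**Working it through.** **Inputs from the documents.** Event rate φ = 0.10; 1,000 test participants; 100 events expected (SAP 6.3; protocol Data Analysis and Appendix B); AUC threshold 0.75 (SAP 5.2, 6.4); α = 0.05 (SAP 7.2).

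**The plan's own figures.** 1,000 × 0.10 = 100 events. Calculation 1, in the form printed in protocol Appendix B: (1.96/0.05)² × 0.1 × 0.9 = 138.3, rounded up to 139, as stated. The factor 0.1 × 0.9 = 0.09 in that formula is the same quantity as the no-information Brier score. The documents state no Brier value other than 0 and 1.

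**Constant predictions (no modelling assumption).** Brier = φ(1−c)² + (1−φ)c² when everyone is assigned risk c:

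- c = 10%: 0.1 × 0.81 + 0.9 × 0.01 = 0.090
- c = 0%: 0.100
- c = 20%, risk overstated twofold: 0.1 × 0.64 + 0.9 × 0.04 = 0.100
- c = 50%: 0.250

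The reference φ(1−φ) shifts with the event rate: 0.0196 at 2%, 0.0475 at 5%, 0.1275 at 15% (assumed rates). The sampling standard error of the 0.090 score with 1,000 participants is √(0.8² × 0.09/1,000) = 0.0076.

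**Models that rank participants (illustrative).** Assume true risk p is logit-normal with mean 0.10, its spread set to give the stated AUC. For a prediction q, Brier = E[p(1−p)] + E[(q−p)²]. The first term reflects event rate and discrimination; the second is the penalty for miscalibration. Tripling the odds, or dividing them by three, leaves the AUC unchanged.

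| Model | Mean prediction | Brier | Scaled, 1 − Brier/0.09 |
|---|---|---|---|
| AUC 0.75, calibrated | 10% | 0.082 | 0.09 |
| AUC 0.80, calibrated | 10% | 0.077 | 0.15 |
| AUC 0.80, odds tripled | 21.6% | 0.0768 + 0.0196 = 0.096 | −0.07 |
| AUC 0.85, odds divided by three | 4.4% | 0.0701 + 0.0076 = 0.078 | 0.14 |

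The last model understates risk by more than half on average, yet scores better than the calibrated AUC 0.75 model. In the tripled-odds case, 9.6% of participants exceed a predicted 50%, against 1.6% if calibrated. Their mean prediction is 64% and their mean true risk 38%.

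**Could these models pass on AUC?** The Hanley–McNeil standard error with 100 events and 900 non-events is 0.0272 at AUC 0.80 and 0.0246 at AUC 0.85. At 0.80 the lower limit is 0.80 − 1.645 × 0.0272 = 0.755 one-sided and 0.80 − 1.96 × 0.0272 = 0.747 two-sided, so it passes only a one-sided test. At 0.85 it is 0.85 − 1.96 × 0.0246 = 0.802, which passes either way.

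**Would intercept and slope find the fault?** With the predicted log-odds as offset, the calibration intercept is −ln 3 = −1.10 for tripled odds and +1.10 for odds divided by three. Its standard error is roughly 1/√(1,000 × 0.0768) = 0.114 and 1/√(1,000 × 0.0701) = 0.119. Both departures exceed nine standard errors. The slope is 1 in both cases; it is needed for the other common fault, predictions that are too extreme.

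**The case against.** A reader might infer that a useless model could be deployed because 0.09 looks close to perfect. The documents do not support that. A constant prediction has AUC 0.50, which SAP 5.2 grades as poor and which fails the AUC condition. Nor do they set a Brier cut-off, so it cannot be said that any value below 0.10 counts as a pass.

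It would also be too strong to call the Brier score blind to calibration. It is a proper score and worsens with miscalibration: tripling the odds at AUC 0.80 moves it from 0.077 to 0.096. Gross error, such as 50% for everyone, would be visible at 0.25.

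The plan has other safeguards. It includes a separate calibration analysis, nested cross-validation in the training data, a search for poorly predicted subpopulations, and comparison models tested on the same participants and so at the same event rate. The SAP's change summary refers to a section 9.5 that is not in the text available, so further calibration detail may exist.

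All of this stands, and it narrows the point. None of it supplies a reference value for the Brier score or a statistic for the calibration condition. Comparison models show which model scores better, not whether its predicted risks are right.

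**Conclusion.** The point holds in a limited form. On the plan's own 10% rate the no-information Brier score is 0.090, and this figure needs no modelling assumption. Read against endpoints of 0 and 1, the raw score cannot show whether a model that has passed on AUC is calibrated. The deployment rule is not void, since its AUC condition still works, but its calibration condition has no adequate measure in the text available.

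The figures for models with discrimination rest on an assumed logit-normal risk distribution and on threefold errors in the odds chosen for illustration. Other assumptions would change their size but not the mixing of discrimination and calibration in one number. The conclusion also assumes that no calibration criterion sits in SAP text not available here. The change should be made before the test cohort is analysed.

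**What to change.** In SAP 5.2 and protocol Stage 2, replace the 0-to-1 benchmark. Report the Brier score beside p(1−p), where p is the event rate observed in the test cohort, and as the scaled score 1 − Brier/[p(1−p)] with a 95% interval.

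In SAP 5.2 and 6.4, judge the calibration condition by the calibration intercept and slope with 95% intervals and a smoothed calibration curve, not by the raw Brier score. State in advance what result counts as reasonable. The scaled score alone is not enough: the AUC 0.85 model with odds divided by three still scores 0.14.

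The cost is wording in both documents and a few lines of code, with no new data. The headline figure becomes less flattering: a calibrated model with AUC 0.75 to 0.80 would show a scaled score of about 9% to 15%, where the raw score would show about 0.08.
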